
Early Safety Data Review:
	
The safety of the CYD dengue vaccine will be continuously monitored by the Sponsor. In the context of this study (ie, HIV-positive adults), a blinded early safety data review (ESDR) will be performed, the goal of which is to allow for a cautious, stepwise approach to vaccine administration. An initial safety review for this study is planned when the first 20 subjects have received the first injection (Inj 1) and have provided safety data for Days 0–14 post-first injection. During the ESDR, study recruitment (and second injection for first 20 subjects, in case the safety review has not been completed at the time of second injection) will be paused.
 
The safety data collected will be entered into the electronic case report book (CRB), and will be summarized and reviewed by the Sponsor. The safety evaluation team (SET) will conduct a blind review of the safety data. It is understood that this review will be based on preliminary data that have not been subject to validation and database lock. The SET will prepare a recommendation that will be reviewed by the IDMC. The IDMC will also review the safety data and then provide recommendation as to whether vaccination of the first enrollees and the enrollment of remaining subjects should resume or not. The ESDR will be assessing the following safety parameters:
 
 • Immediate (within 30 minutes) AEs • Solicited injection site and systemic reactions • Unsolicited AEs reported as related by the Investigator within 14 days after the first injection • SAEs and AESIs (including serious and non-serious AESIs) 
Case unblinding may be performed if required. Some unblinded analyses may be provided by an independent Sanofi Pasteur statistician (ie, not involved either in the study or in the Dengue project) upon IDMC request.
 
The decision regarding the continuation of vaccination of the 20 first enrollees and of the remaining 130 subjects will be communicated to the Investigators and will be sent

	
to the Independent Ethics Committees (IECs)/Institutional Review Boards (IRBs) and the IDMC for information.

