
Primary Objective:	
Safety
 
 • To describe the safety of each injection of CYD dengue vaccine in HIV-positive adults previously exposed to dengue
Primary Endpoints:	
Safety
 
 • Occurrence of any unsolicited systemic AE reported within 30 minutes after each injection • Occurrence of solicited (ie, pre-listed in the subject's diary card [DC] and in the CRB) injection site reactions (pain, erythema, and swelling) occurring up to 7 days after each injection • Occurrence of solicited systemic reactions (fever, headache, malaise, myalgia, and asthenia) occurring up to 14 days after each injection • Occurrence of unsolicited AEs occurring up to 28 days after each injection • Occurrence of serious and non-serious AESIs in defined time windows according to the type of AESI • Occurrence of SAEs throughout the study (ie, from D0 through the end of the study) • Occurrence of hospitalized VCD cases throughout the study (ie, from D0 through the end of the study) 
Other endpoints will be recorded or derived as described in the Statistical Analysis Plan. Depending on the item, these could include: nature (Medical Dictionary for Regulatory Activities [MedDRA] preferred term), time of onset, duration, number of days of occurrence, intensity, relationship to vaccine, action taken, whether the event/reaction led to early termination from the study, seriousness, or outcome. Hospitalized suspected dengue disease is defined as an acute febrile illness with diagnosis of dengue requiring hospitalization (inpatient care). In such cases, 1 unplanned acute blood sample (within the first 5 days after fever onset) will be collected for virological confirmation of dengue disease. A suspected case will be considered VCD if there is a detection of wild-type (WT) dengue virus by dengue non-structural protein (NS) 1 antigen (Ag) enzyme-linked immunosorbent assay (ELISA) and/or dengue reverse transcriptase-polymerase chain reactions (RT-PCRs) (at the Global Clinical Immunology [GCI] or GCI designated laboratory). Note: Acute blood sample for all suspected hospitalized dengue cases should be collected within the pre-specified timeframe as described above. If this cannot be accomplished, this sample should still be obtained as soon as possible thereafter, for IDMC severity assessment

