Medical and scientific judgment should be exercised in deciding whether expedited reporting is appropriate in other situations, such as IMEs that may not be immediately life-threatening or result in death or hospitalization but may jeopardize the health of the subject or may require intervention to prevent one of the other outcomes listed in the definition above. These IMEs should also usually be considered serious. Examples of such events include allergic bronchospasm requiring intensive treatment in an emergency room or at home, blood dyscrasias or convulsions that do not result in inpatient hospitalization, or the development of drug dependency or drug abuse, new-onset diabetes, or autoimmune disease.

Adverse reaction:

All noxious and unintended responses to a medicinal product related to any dose should be considered AR.

(The phrase “responses to a medicinal product” means that a causal relationship between a medicinal product and an AE is at least a reasonable possibility)

The following additional definitions are used by Sanofi Pasteur:

Immediate event/reaction:

Immediate events are recorded to capture medically relevant unsolicited systemic AEs (including those related to the product administered) that occur within the first 30 minutes after vaccination.

Solicited reaction:

A solicited reaction is an “expected” adverse reaction (sign or symptom) observed and reported under the conditions (nature and onset) pre-listed in the protocol and CRB (eg, injection site pain between D0 and D7 post-vaccination, or headache between D0, and D7).

By definition, solicited reactions are to be considered as being related to the product administered.

For injectable vaccines, solicited reactions can either be solicited injection site reactions or solicited systemic reactions.

^a The term “life-threatening” refers to an event in which the subject was at risk of death at the time of the event; it does not refer to an event which hypothetically might have caused death if it were more severe.

^b All medical events leading to hospitalizations will be recorded and reported as SAEs, with the exception of: hospitalization planned before inclusion into the study or outpatient treatment with no hospitalization.

^c “Persistent or significant disability or incapacity” means that there is a substantial disruption of a person’s ability to carry out normal life functions.

Unsolicited AE / AR:

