An unsolicited AE is an observed AE that does not fulfill the conditions pre-listed in the CRB in terms of diagnosis and/or onset window post-vaccination. For example, if headache between D0 and D7 is a solicited reaction (ie, pre-listed in the protocol and CRB), then a headache starting on D7 is a solicited reaction, whereas headache starting on D8 post-vaccination is an unsolicited AE. Unsolicited AEs includes both serious (SAEs) and non-serious unsolicited AEs.

Injection site reaction:

An injection site reaction is an AR at and around the injection site. Injection site reactions are commonly inflammatory reactions. They are considered to be related to the product administered.

Systemic AE:

Systemic AEs are all AEs that are not injection or administration site reactions. They therefore include systemic manifestations such as headache, fever, as well as localized or topical manifestations that are not associated with the vaccination or administration site (eg, erythema that is localized but that is not occurring at the injection site).

Adverse event of special interest (AESI):

An adverse event of special interest is one of scientific and medical concern specific to the Sponsor's product or program, for which ongoing monitoring, and rapid communication by the Investigator to the Sponsor can be appropriate. Such an event might warrant further investigation in order to characterize and understand it. Depending on the nature of the event, rapid communication by the study Sponsor to other parties (eg, regulators) might also be warranted.

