9.1.1.3.5 Assessment of Causality

The Investigator will assess the *causal relationship* between each unsolicited systemic AE and the product administered as either *not related* or *related*, based on the following definitions:

Not related – The AE is clearly / most probably caused by other etiologies such as an underlying condition, therapeutic intervention, or concomitant therapy; or the delay between vaccination and the onset of the AE is incompatible with a causal relationship; or the AE started before the first vaccination (screening phase, if applicable)

Related – There is a “reasonable possibility” that the AE was caused by the product administered, meaning that there is evidence or arguments to suggest a causal relationship

Note: By convention, all AEs reported at the injection site (whether solicited or unsolicited) and all solicited systemic AEs are considered to be related to the administered product and therefore are referred to as reactions and do not require the Investigator’s opinion on relatedness.

Adverse events likely to be related to the product, whether serious, or not, that persist at the end of the study will be followed-up by the Investigator until their complete disappearance or the stabilization of the subject’s condition. The Investigator will inform the Sponsor of the date of final disappearance of the event or the date of “chronicity” establishment.

9.1.1.4 Methods for Virological Confirmation of Suspected Dengue Disease and Assessment of Disease Severity

In the event of a suspected hospitalized dengue case, the following tests will be performed based on the process described below.

Dengue Screen RT-PCR

Dengue screen RT-PCR test will be performed by Sanofi Pasteur GCI, Swiftwater, USA or GCI designated laboratory.

Assessment and quantitation of dengue viremia is determined by testing serum samples with a nucleic-acid based assay. RNA is extracted from the serum to discard potential Taq polymerase inhibitors or interfering factors, using a commercial kit. Then, a RT-PCR is carried out with primers from a gene sequence conserved among dengue viruses. Due to a virus standard included in each run, results can be expressed as a concentration of log10 plaque forming unit (PFU)/mL.

Simplexa™ Dengue RT-PCR

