5.6 Data Review for Statistical Purposes

A treatment blind review of the data has been anticipated through the data review process led by data management before database lock. This review of the data included a statistical review.

In the context of this study (ie, HIV-positive adults), a blinded early safety data review will be performed when the first 20 subjects have received the first injection and have provided safety data for Days 0-14 post-first injection on the following safety endpoints:

- Immediate (within 30 minutes) AEs
- Solicited injection site and systemic reactions
- Unsolicited AEs reported as related by the investigator within 14 days after the first injection
- SAEs and AESIs (including serious and non-serious AESIs)

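### Apart from immediate AEs, SAEs and AESIs, the early safety review lists unsolicited AEs only if the blinded investigator called them related, so other non-serious systemic events put down to HIV, ART or another cause are not on its list

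*Protocol*

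**What the plan says.** The ESDR takes place once 20 subjects have had injection 1 and given safety data to Day 14. The internal safety team reviews the data blinded and drafts a recommendation. The IDMC also reviews the safety data and recommends whether enrolment and vaccination resume. The list of parameters is the same in the Protocol Synopsis (Early Safety Data Review), Protocol 5.1.6 and SAP 5.6. It has four items:

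- "Immediate (within 30 minutes) AEs"
- the pre-listed (solicited) reactions, local as well as general
- "Unsolicited AEs reported as related by the Investigator within 14 days after the first injection" (SAP 5.6: "Unsolicited AEs reported as related by the investigator within 14 days after the first injection")
- "SAEs and AESIs (including serious and non-serious AESIs"

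Only the third item depends on causality. Protocol 9.1.1.3.5 has the investigator call an event not related when it is clearly or most probably "caused by other etiologies such as an underlying condition, therapeutic intervention, or concomitant therapy", among other grounds. Related requires only a reasonable possibility. Under Protocol 6.4 the observing investigator is blinded.

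The primary endpoint (Synopsis; Protocol 9.1.1.2) carries no causality condition: "Occurrence of unsolicited AEs occurring up to 28 days after each injection".

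**The concern.** The ESDR is the only scheduled early look before 130 further subjects receive a first dose of a live vaccine or placebo. Protocol 1.4 says the vaccine has so far been tested on healthy people, with at-risk populations left out. There is therefore little experience in HIV-positive adults on which to base a causality call. Every subject has HIV and takes ART, so an underlying condition and a concomitant therapy are always available as candidate explanations.

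The hold criteria in Protocol 5.5 do not cover this gap. They concern related Grade 3 solicited systemic reactions, related SAEs, HIV viral load and CD4 count. None responds to non-serious unsolicited events. An unexpected non-serious effect that the investigator put down to HIV or ART could therefore be recorded in the case report book and still be missing from the listed review data.

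**Working it through.** **Which events are on no line of the list**

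| Type of event, Days 0–14 after injection 1 | Listed if called not related? | Source |
|---|---|---|
| Unsolicited systemic, within 30 minutes | Yes, as an immediate AE | Protocol 9.1.1.1: "Immediate events are recorded to capture medically relevant unsolicited systemic AEs (including those related to the product administered" |
| Serious | Yes, as an SAE | Protocol 9.1.1.1: "Unsolicited AEs includes both serious (SAEs) and non-serious unsolicited AEs" |
| Non-serious allergic reaction within 7 days | Yes, as an AESI | Protocol 9.1.1.3.4 |
| Fever, headache, malaise, myalgia, asthenia | Yes; solicited and related by convention | Protocol 9.1.1.2, 9.1.1.3.5 |
| Injection site event, solicited or not | Not applicable; related by convention | Protocol 9.1.1.3.5 |
| Any other non-serious systemic event | **No** | – |

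The gap is the last row.

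A smaller ambiguity is that the ESDR uses uncleaned data (Protocol 5.1.6). SAP 5.3.1.2 treats missing causality as related at the time of analysis but does not say whether that applies to this review.

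**The plan's own detection figure.** Protocol 12.5 and SAP 5.5 state a 95% probability of observing an event of 3% incidence with 100 vaccinees. 1 − 0.97^100 = 0.952, so the figure reproduces. No such figure is stated for the ESDR.

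**The same calculation for the ESDR**

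- Vaccinees among the first 20 at 2:1: 20 × 2/3 = 13.3, taken as 13.
- At 3% incidence with no filter: 1 − 0.97^13 = 0.33.
- Incidence needed for 95% detection with no filter: 1 − 0.05^(1/13) = 20.6%.

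**Effect of the filter.** Let p be the incidence of a vaccine-caused event of the type in the last row, and q the share of such events called related. The chance that at least one is listed is 1 − (1 − pq)^13. The documents give neither p nor q, so both are assumptions.

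For p = 15%:

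| q | pq | Chance at least one is listed |
|---|---|---|
| 1 (no filter) | 0.150 | 1 − 0.850^13 = 0.88 |
| 0.7 | 0.105 | 1 − 0.895^13 = 0.76 |
| 0.5 | 0.075 | 1 − 0.925^13 = 0.64 |
| 0.3 | 0.045 | 1 − 0.955^13 = 0.45 |
| 0.1 | 0.015 | 1 − 0.985^13 = 0.18 |

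For other incidences, at q = 1, 0.5 and 0.25:

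- p = 5%: 0.49, 0.28, 0.15
- p = 10%: 0.75, 0.49, 0.28
- p = 20%: 0.95, 0.75, 0.49

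The direction needs no assumption: any q below 1 lowers the chance.

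**The case against.** The strongest reply is that the gap is narrow and the filter a reasonable choice. Serious, allergic, immediate, injection site and common systemic events all reach the review. Not related has a high threshold and related a low one. Protocol 5.2.4 requires at least a year of stable HIV condition and stable ART before consent, so a new event within 14 days of an injection is not easily blamed on an unchanged regimen. The final analysis reports all unsolicited AEs, and an early check may use a focused dataset. Protocol and SAP agree with each other. Later safeguards also exist: the hold rules, IDMC review of related SAEs and deaths, and contraindication checks before each further injection.

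Most of this stands. It limits the size of the gap and argues against any assumption that q is low, but it does not close the gap.

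A reader might infer more than the documents support:

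- **That the IDMC is kept from seeing these events.** Nothing bars it. The list says what the ESDR assesses, the IDMC reviews the safety data, and it may request unblinded analyses or code-breaking (Protocol 5.1.6, 6.4).
- **That tables by arm would be limited to related events.** No text says so.
- **That such events would most likely be called unrelated.** The documents give no attribution rate, and the thresholds above point the other way.
- **That a comparison by arm could replace causality judgement.** It could not at this size. With about 13 vaccinees and 7 placebo subjects, 2 events against 0 gives a one-sided Fisher p of C(13,2)/C(20,2) = 78/190 = 0.41.

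**Conclusion.** The point holds as a gap in the review's default content. Non-serious systemic unsolicited AEs that start after 30 minutes, are not AESIs and are called not related are on no ESDR line, and nothing brings them to the IDMC unless it asks. A committee is less likely to ask about events it has not been shown.

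The size cannot be fixed from the documents. The fall from 88% to between 76% and 18% rests on 13 vaccinees, an assumed 15% incidence, an assumed attribution share of 70% down to 10%, and independence between subjects. The ESDR states no decision threshold, so seeing one such event would not in itself change the recommendation. No figure in the plan is wrong and the documents do not contradict each other. This is an inexpensive improvement to a small dataset.

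**What to change.** In the Protocol Synopsis, Protocol 5.1.6 and SAP 5.6, replace the third item with all unsolicited AEs starting in Days 0–14 after injection 1, with the investigator's causality shown as a column and missing causality shown as missing. State that the same unfiltered set is the basis for any analysis by arm that the IDMC requests.

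The cost is a few more listing lines for 20 subjects, mostly background events that the reviewers must read past. No new collection is needed. AEs are already recorded at Visits 2 and 3, and relatedness is already captured for each unsolicited systemic AE (Protocol 5.1.4, 9.1.1.3.3).

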1.1 Background

This is a Phase II study assessing the safety and immunogenicity of the CYD dengue vaccine when administered in Human Immunodeficiency Virus (HIV)-positive adults, previously exposed to dengue, with clinically-stable condition under regular antiretroviral therapy (ART).

Dengue

Dengue disease is caused by 4 closely related, but antigenically distinct, dengue virus serotypes (1, 2, 3, and 4) of the genus flavivirus (FV). Infection with a dengue virus is usually asymptomatic but can produce a spectrum of clinical illnesses ranging from a non-specific viral syndrome to severe, fatal hemorrhagic disease (1-4). Dengue fever (DF) is characterized by biphasic fever, headache, and myalgia in various parts of the body, prostration, rash, and lymphadenopathy. Recovery from DF is usually complete in 7 to 10 days, but prolonged asthenia is common. Decreases in leukocytes and platelets count are frequent. The incubation period of DF after the mosquito bite averages 4 days (range from 3 to 14 days) (2).

Dengue hemorrhagic fever (DHF) is characterized by abnormalities of homeostasis and increased vascular permeability that can lead to hypovolemia and hypotension (dengue shock syndrome), often complicated by severe internal bleeding. The case fatality rate of severe dengue can be as high as 20% without medical care, but is below 1% in most centers with modern intensive supportive therapy (2).

Human infection occurs by injection of the virus into the extravascular tissues during blood feeding by an infected *Aedes aegypti* mosquito or *Aedes albopictus* mosquito (1). Both these vectors are now present in all tropical and sub-tropical areas of the world and in some temperate areas of the USA, Europe, Africa, and the Middle East. Following its rapid spread in recent years, DF/DHF is now endemic/epidemic in Latin America, South East Asia, India, Africa, and the Caribbean, and Pacific regions.

According to the World Health Organization (WHO), over 2.5 billion people are now at risk from dengue in more than 100 countries in Africa, the Americas, the Eastern Mediterranean, South East Asia, and the Western Pacific. The Americas, South East Asia, and the Western Pacific regions are the most seriously affected. It is currently estimated that there may be 390 million dengue infections worldwide every year. An estimated 500 000 people with severe dengue require hospitalization, a large proportion of whom are children. About 2.5% of those affected die (2). Thus, according to WHO, there is an urgent need to develop a safe and effective method to prevent progression of this substantial public health issue (2) (3).

Routine laboratory diagnosis of dengue infection is based on the detection of dengue virus-specific antibodies (Abs), immunoglobulin (Ig) M and/or isolation of the virus or detection of viral ribonucleic acid (RNA) by reverse transcription-polymerase chain reaction (RT-PCR) or viral non-structural protein (NS) 1 antigen by enzyme-linked immunosorbent assay (ELISA) (4-6). The diagnosis of dengue falls into 2 stages: Stage I, the acute fever period lasting a few days when viremia may be detected; and Stage II, the early post-febrile period lasting a few weeks when IgM and IgG Abs are increased.

Until recently, vector control, and personal protection were the only measures to prevent dengue infection and disease. Although some prevention and vector control campaigns are well-documented successes, most of these successes have proved to be temporary as public health authorities were unable to sustain underlying control strategies in the face of social and/or environmental changes (7). It is now increasingly acknowledged that eliminating dengue as a public health burden will involve a safe and effective vaccine directed at the 4 serotypes of dengue virus responsible for the disease, in addition to preventive measures (7).

Human Immunodeficiency Virus

The HIV belongs to the family of retrovirus. It can be transmitted from human to human mostly through sexual intercourses, needle sharing among injecting drug users, and from mother to child during pregnancy (8).

During infection, virus particles bind to host cells expressing principally CD4 receptors but also a range of host proteins (9). The hallmark of HIV infection is the progressive depletion of CD4+ T cells (CD4) leading, after a highly variable period of time, to the acquired immune deficiency syndrome (AIDS). At this stage, the HIV infection becomes symptomatic and the infected person experiences opportunistic infections, eventually leading to death.

The development of ARTs regimen during the past 2 decades has transformed HIV infection from a progressive illness with a fatal outcome into a chronic manageable disease. In parallel, and following extensive national prevention campaigns, remarkable progresses have been made in terms of prevention-associated risk reduction. As for the development of an efficacious HIV vaccine, it is still facing important challenges, including the virus's genetic diversity, uncertainty about what constitutes protective immunity, and difficulty in the development of antigens that are highly immunogenic (8).

Despite advances on complementary fronts, HIV infection remains endemic worldwide, with higher incidence in low-income and middle-income countries, as a consequence of a limited access to health care (Asia, Sub-Saharan Africa, and Latin America). Globally, the number of new infections has decreased between 2000 and 2018. However, global prevalence of HIV has increased from 27.4 (23.1–32.6) million to 37.9 (32.7–44.0) million during the same period as ART has increased life expectancy of infected persons (10). In 2017, an estimated (10):

- 37.9 million (32.7 million–44.0 million) people globally were living with HIV
- 1.7 million (1.4 million–2.3 million) people became newly infected with HIV
- 770 000 (570 000–1.1 million) people died from AIDS-related illnesses

Dengue and HIV co-infection

Interactions between HIV and other infectious agents, particularly in tropical regions, has been associated with accelerated HIV/AIDS disease progression (11). However, the severity and characteristics of dengue and HIV co-infection and the reciprocal impact on disease progression remain elusive because of lack of systematic case-control analysis (12-14). An increased risk of severe dengue has not been described in HIV-positive subjects, but there are very limited data (11) (14-17). Thus far, case series have suggested that patients with dengue virus (DENV)-HIV co-infection have non-severe dengue outcome (18) and show no signs of accelerated progression of HIV disease (12-14). This may be due to the transient reduction of HIV viral load and no depletion of CD4+ T cells during acute dengue infection, plus the likely beneficial effect of the ART on the dengue infection course (13) (14) (17). Furthermore, it has also been observed that the DEN-2 NS5 protein inhibits HIV replication in CD4+ T cells in vitro (19). However, further research is still needed to understand DENV-HIV co-infection, especially since the number of cases is bound to increase in the coming years as life expectancy of HIV-positive persons increases.

